10.2. Monitoring, Recording and Reporting of AEs

[name]., is the principal investigator of this study; The University of Arkansas for Medical Sciences (UAMS) is the study sponsor. UAMS is responsible for reporting serious adverse events (SAEs) to any regulatory agency; the principal investigator is responsible for reporting to the IRB and other entities (see Section 10.4).

AEs may be spontaneously reported by the patient and/or in response to an open question from study personnel or revealed by observation, physical examination, or other diagnostic procedures. When possible, signs and symptoms indicating a common underlying pathology should be noted as one comprehensive event. All AEs occurring during the study period must be recorded. The clinical course of each event should be followed until resolution, stabilization, or until it has been determined that the study treatment or participation is not the cause. SAEs that are still ongoing at the end of the study period must be followed up for up to 30 days to determine the final outcome. Any SAE that occurs after the study period and is considered to be possibly related to the study treatment or study participation should be recorded and reported immediately to the Sponsor (UAMS).

All subjects will be monitored for AE's during the study. Assessments may include monitoring the patient's clinical symptoms; laboratory, pathological, radiological, or surgical findings; physical examination; or other appropriate tests and procedures.

Planned hospital admissions or surgical procedures for an illness or disease that existed before the patient was enrolled in the trial are not to be considered AEs unless the condition deteriorated in an

unexpected manner during the trial (e.g., surgery was performed earlier or later than planned). All SAEs should be monitored until they are resolved or are clearly determined to be due to a patient's stable or chronic condition or intercurrent illness(es).

AE's are to be reported in a routine fashion at scheduled times during the trial, such as with the annual continuing review to the IRB. Certain AEs must be reported in an expedited manner to allow for more timely monitoring of subject safety and care. The preporting of these events depends on the characteristics of the event:

- Seriousness (grading of event)
- Relatedness to study therapy
- Expectedness

Steps to Determine if the event requires expedited Reporting:

- Identify the type of event and grade the event using NCI CTCAE version 4.0
- Determine whether the adverse event is related to the investigational drug. Attribution categories are as follows:
 - Unrelated
 - o Unlikely
 - Possible
 - o Probable
 - Definite
- Determine the expectedness of the event. Expected events are those previously identified resulting from administration of the agent. See definition for "unexpected" above.

10.3. Expedited Reporting of SAEs

Only adverse events meeting the UPIRTSO (Unanticipated Problem Involving Risks to Subjects or Others) will need to be reported to the UAMS IRB within the required 10 day period of being notified of the event. UPIRTSO requires that an unanticipated problem meet the following qualifications: a) unanticipated or unexpected; b) related to the research; and c) involves new or increased risk to the subject(s). All other adverse events should be recorded and reported to the UAMS IRB at continuing review.

The Sponsor (UAMS) will be promptly notified of all SAEs that are related to the study and unanticipated/unexpected. These SAEs will be reported to the Sponsor using the FDA Medwatch 3500A. UAMS will report events to FDA in accordance with 21CFR312.

All other SAEs will be reported to the Sponsor and FDA in the Annual Progress Report.

Deaths that are related to research will be reported to the Sponsor immediately upon Investigator notification. A death due to a terminal condition of the research participant would be considered anticipated and not related to the research and therefore not immediately reportable under this policy. The sponsor will report deaths to FDA in accordance with 21CFR312.

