intervention to prevent 1 of the outcomes listed above, or involves suspected transmission via a medicinal product of an infectious agent. Examples of such medical events include allergic bronchospasm requiring intensive treatment in an emergency room or at home, blood dyscrasias or convulsions that do not result in inpatient hospitalization, or the development of drug dependency or drug abuse; any organism, virus, or infectious particle (eg, prion protein transmitting Transmissible Spongiform Encephalopathy), pathogenic or nonpathogenic, is considered an infectious agent.

Clarification should be made between a serious AE (SAE) and an AE that is considered severe in intensity (Grade 3 or 4), because the terms serious and severe are NOT synonymous. The general term *severe* is often used to describe the intensity (severity) of a specific event; the event itself, however, may be of relatively minor medical significance (such as a Grade 3 headache). This is NOT the same as *serious*, which is based on patient/event outcome or action criteria described above, and is usually associated with events that pose a threat to a patient's life or ability to function. A severe AE (Grade 3 or 4) does not necessarily need to be considered serious. For example, a white blood cell count of 1000/mm³ to less than 2000 is considered Grade 3 (severe) but may not be considered serious. Seriousness (not intensity) serves as a guide for defining regulatory reporting obligations.

Related

An event is "related" if more likely than not it was caused by the study drug

Unexpected

An event is "unexpected" when its specificity, nature, severity or incidence is not accurately reflected in the consent form, protocol, or IB previously reviewed and approved by the IRB. Examples include lower rate of response to treatment or a side effect that is more severe than initially expected.

Study Period

The study period is defined as the period of time from start of study drug through the End of Treatment visit. Events occurring after enrollment but prior to the study period will be considered pretreatment events (see above).

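### Section 10.3 leaves related, expected, non-fatal SAEs on treatment, even life-threatening ones, to the annual report for the IND sponsor, out of step with the immediate rule in 10.2

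*Combined protocol and SAP*

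**What the plan says.** Section 10.3 sets two fast routes from the investigator to the IND sponsor. The first is for SAEs that pass two tests together: "The Sponsor (UAMS) will be promptly notified of all SAEs that are related to the study and unanticipated/unexpected". The form is fixed ("These SAEs will be reported to the Sponsor using the FDA Medwatch 3500A"), but no number of days is given. The second is for deaths: "Deaths that are related to research will be reported to the Sponsor immediately upon Investigator notification". Everything else falls to a default: "All other SAEs will be reported to the Sponsor and FDA in the Annual Progress Report".

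Section 10.2 has a separate rule for SAEs after the study period. Those "considered to be possibly related to the study treatment or study participation should be recorded and reported immediately to the Sponsor (UAMS" are not put to any test of expectedness. Section 10.1 defines the study period as running "from start of study drug through the End of Treatment visit".

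Section 10.4 covers reports to the drug supplier. All SAEs from consent to 30 days after the last dose go to it, whatever their cause or expectedness. The limit is 4 calendar days, with a 24-hour target for fatal or life-threatening events.

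**The concern.** Under 10.2, "UAMS is responsible for reporting serious adverse events (SAEs) to any regulatory agency". The same section gives the purpose of fast reporting: "Certain AEs must be reported in an expedited manner to allow for more timely monitoring of subject safety and care". Yet for one class of event, related and already known but serious, the only stated route to UAMS during treatment is a yearly document.

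The class is not trivial. Section 8.2.5 says that thrombocytopenia and neutropenia may be severe. Section 1.3 lists pneumonia, and acute renal failure that in one case needed temporary dialysis. Events such as these can be serious, related and expected all at once. At stake is whether the accountable sponsor could notice a run of known but serious toxicities while patients are still being treated.

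**Working it through.** The plan gives no figure to reproduce. The check compares the rules, followed by arithmetic on the delay.

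**1. One event, three rules.** Take a related, expected, life-threatening but non-fatal SAE.

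| Timing | Recipient | Section | Deadline |
|---|---|---|---|
| On treatment | UAMS | 10.3 | Annual Progress Report |
| On treatment | Supplier | 10.4 | Target 24 hours, at most 4 calendar days |
| After End of Treatment visit | UAMS | 10.2 | Immediately |
| After End of Treatment visit | UAMS | 10.3, read literally | Annual Progress Report |

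Rows 1 and 3 have the same recipient and the same event, but the deadline changes at the End of Treatment visit. Rows 3 and 4 collide outright: the default in 10.3 has no time limit, so a related, expected SAE after that visit falls under both an immediate and an annual rule.

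**2. Does the definition of unexpected rescue the class?** Section 10.1 lets an event count as unexpected if its nature, specificity, severity or incidence is not accurately reflected in the consent form, protocol or Investigator's Brochure. Severity will not readily catch events that the protocol already calls potentially severe. Incidence might catch a case of Stevens-Johnson syndrome, which 8.2.5 lists as rare. The definition narrows the class but does not empty it.

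**3. Length of the delay.** On an annual cycle the longest wait is 12 months. The planned course is 6 × 28 = 168 days, and 168 / 30.4375 = 5.52 months, so the wait can outlast the course.

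For illustration, assume 20 patients accrued evenly over the 20 months in Section 4.3 (starts at months 0 to 19, or 0.5 to 19.5), full 168-day courses, and annual reports at months m, m + 12 and m + 24, with m anywhere from 1 to 12.

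- Reports by month 20: 2 if m ≤ 8, otherwise 1.
- Reports by month 26: 3 if m ≤ 2, otherwise 2.
- Patients with no annual report between first dose and end of course: 8 to 13 of 20. The long-run share is (12 − 5.52) / 12 = 54%.
- Mean wait from a random treatment day to the next report: 5.54 to 6.46 months.

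These figures describe the calendar only. They count patients, not affected SAEs, and early stopping for progression or toxicity would change them.

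**The case against.** **The tiering is deliberate.** Section 10.2 says that expedited reporting depends on seriousness, relatedness and expectedness, and 10.3 applies that. This stands as an explanation of the design. It does not explain why the expectedness test disappears once treatment ends. A catch-all makes sense after routine AE recording stops, but it still leaves two incompatible rules for the same later event.

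**Section 10.4 is not in conflict.** A reader might infer that 10.3 contradicts 10.4. It does not: 10.4 has a different recipient and adds a duty to the others. Its relevance is practical, because the report, the form and the clock are already in use.

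**Other duties may apply.** A reader might also infer that nothing obliges faster notice. The documents do not support that. Section 12.4 places investigator responsibilities in GCP and the federal regulations, 1.3 commits the study to GCP and applicable requirements, and 12.2 requires notice to the sponsor of anything that may add risk. What the outside rules require cannot be checked here. The supportable statement is that Section 10 itself sets no faster clock and that 12.2 gives no deadline. For the same reason, no breach of 21CFR312 is claimed.

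**The consequence is limited.** This largely stands. The investigator works within the sponsor institution, and the title page makes their obligations joint. Dose holds and reductions under 8.2.3 do not wait for sponsor notice. No stopping rule based on SAE counts would be triggered earlier. Section 12.6 allows suspension but names no SAE trigger and no decision-maker. It would be wrong to read the gap as an absence of safety oversight, or to say that care of an individual patient depends on when the annual report falls.

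**Conclusion.** The point holds in a narrow form. For related, expected, non-fatal SAEs on treatment, including life-threatening ones, the only timing that Section 10 gives for notice to UAMS is the annual report. This is inconsistent with 10.2, and after the End of Treatment visit the two sections conflict directly.

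The delay is up to 12 months, which assumes only an annual cycle. The patient counts and mean waits above rest further on assumed report dates, even accrual and full courses, and should be taken as illustration. The number of affected SAEs is unknown: the documents give no SAE rate, and the Investigator's Brochure and consent form that help to define expectedness are not available.

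No excess-exposure argument should be attached to this point. Using the plan's equivalence of 4.0 mg to 2.23 mg/m², exposure per 28 days is 4 × 2.23 = 8.92 mg/m², against 3 × 2.97 = 8.91 mg/m² at the weekly single-agent MTD in C16004. Only the missing rest week is new.

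This is a cheap improvement of low severity.

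**What to change.** Replace the default sentence in 10.3 with:

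> All SAEs from informed consent through 30 days after the last dose, regardless of expectedness or causality, will be sent to the Sponsor (UAMS) no later than the Section 10.4 timelines, on the same form or MedWatch 3500A; related and unexpected SAEs will be sent promptly and in any case within those timelines, and related deaths immediately. Possibly related SAEs after the study period are reported immediately under Section 10.2. Any other SAE, and any SAE not requiring expedited reporting to FDA under 21CFR312, will be included in the Annual Progress Report.

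This wording puts an outer limit on the undefined prompt notice, so that the most important SAEs do not end up with the vaguest deadline. It states that 10.2 governs after the study period, and it keeps a route to UAMS for unrelated SAEs outside the 10.4 window. The IRB rules and the tiering of reports to FDA stay as they are.

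The cost is a small amount of extra reporting to UAMS, including some unrelated and pretreatment SAEs. A difference at the End of Treatment visit remains, but it becomes at most 4 calendar days against immediate, instead of up to 12 months.

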10.4. Other Required Reporting

AEs which are serious must be reported to Millennium Pharmacovigilance (or designee) from the date the participant signs Informed Consent through 30 days after administration of the last dost of ixazomib. Any SAE that occurs at any time after completion of ixazomib treatment or after the study period that the principal-investigator and/or sub-investigator considers to be related to any study drug must be reported to Millennium Pharmacovigilance (or designee). In addition, new primary malignancies that occur during the follow-up periods must be reported, regardless of causality to study regimen, for a minimum of three years after the last dose of the investigational product, starting from the first dose of study drug. All new cases of primary malignancy must be reported to Millennium Pharmacovigilance (or designee). Regardless of expectedness or causality, all SAEs (including serious pretreatment events) must also be reported to Millennium Pharmacovigilance:

Fatal and Life Threatening SAEs within 24 hours but no later than 4 calendar days of the investigator's observation or awareness of the event

All other serious (non-fatal/non-life threatening) events within 4 calendar days of the investigator's observation or awareness of the event

See below for contact information for the reporting of SAEs to Millennium Pharmacovigilance.

The investigator must fax the SAE Form per the timelines above. A sample of an SAE Form will be provided.

The SAE report must include at minimum:

Event term(s)

Serious criteria

Intensity of the event(s): Principal- or sub-investigator's determination. Intensity for each SAE, including any lab abnormalities, will be determined by using the NCI CTCAE version specified in the protocol, as a guideline, whenever possible. The criteria are available online at http://ctep.cancer.gov/reporting/ctc.html.

Causality of the event(s): Principal- or sub-investigator's determination of the relationship of the event(s) to study drug administration.

Follow-up information on the SAE may be requested by Millennium.

Intensity for each SAE, including any lab abnormalities, will be determined by using the NCI CTCAE version 4.0, as a guideline, whenever possible. The criteria are available online at http://ctep.cancer.gov/reporting/ctc.html.

Relationship to the study drugs for each SAE will be determined by the investigator or sub-investigator by responding yes or no to the question: Is there a reasonable possibility that the AE is associated with the study drug(s)?

The investigator must also provide Millennium Pharmacovigilance with a copy of all communications with applicable regulatory authorities related to the study product(s), as soon as possible but no later than 4 calendar days of such communication.

SAE and Pregnancy Reporting Contact Information

SAE and Pregnancy Reporting Contact Information

[contact] Email: [contact]

Suggested Reporting Form:

- SAE Report Form (if provided by Millennium)
- US FDA MedWatch 3500A: http://www.fda.gov/Safety/MedWatch/HowToReport/DownloadForms/default.htm
- Any other form deemed appropriate by the Sponsor and/or Principal Investigator

10.5. Procedures for Reporting Drug Exposure During Pregnancy and Birth Events

If a woman becomes pregnant or suspects that she is pregnant while participating in this study, or within 90 days of the subject's last dose of study drug she must inform the investigator immediately and permanently discontinue study drug. The investigator must immediately fax a completed Pregnancy Form to the Millennium Department of Pharmacovigilance or designee (see above). The pregnancy must be followed for the final pregnancy outcome.

If a female partner of a male patient becomes pregnant during the male patient's participation in this study, the investigator must also immediately fax a completed Pregnancy Form to the Millennium Department of Pharmacovigilance or designee (see above). Every effort should be made to follow the pregnancy for the final pregnancy outcome.

11.ADMINISTRATIVE REQUIREMENTS

11.1. Product Complaints

A product complaint is a verbal, written, or electronic expression that implies dissatisfaction regarding the identity, strength, purity, quality, or stability of a drug product. Individuals who identify a potential product complaint situation should immediately contact MedComm Solutions (see below) and report the event. Whenever possible, the associated product should be maintained in accordance with the label instructions pending further guidance from a Millennium Quality representative.

For Product Complaints, call [name] ([name]) Email: [contact] [contact] Hours: Mon-Fri, 8am-6pm EST

Product complaints in and of themselves are not AEs. If a product complaint results in an SAE, an SAE form should be completed and sent to Millennium Pharmacovigilance.

12. ETHICAL AND REGULATORY CONSIDERATIONS

12.1. Informed Consent

The principles of informed consent are described by Federal Regulatory Guidelines (Federal Register Vol 46, No. 17, January 27, 1981, part 50) and the Office for Protection from Research Risks Reports: Protection of Human Subjects (Code of Federal Regulations 45 CFR 46). They must be followed to comply with FDA regulations for the conduct and monitoring of clinical investigations.

12.2. Institutional Review

This study must be approved by the UAMS Institutional Review Board, as defined by Federal Regulatory Guidelines (Ref Federal Register Vol. 46, No. 17, January 27, 1981, part 56) and the Office for Protection from Research Risks Reports: Protection of Human Subjects (Code of Federal Regulations 45 CFR 46).

The Investigator will be responsible for preparing documents for submission to the relevant IRB/EC and obtaining written approval for this study. The approval will be obtained prior to the initiation of the study.

Any modifications/amendments to the protocol after receipt of IRB/EC approval must be submitted by the Investigator to the IRB/EC for approval and to the sponsor. The Investigator is also responsible for notifying the IRB/EC and sponsor of any serious deviations from the protocol, or anything that may

involve added risk to study subjects.

12.3. Subject Confidentiality

The Myeloma Institute affirms the subject's right to protection against invasion of privacy. In compliance with United States Federal regulations, representatives of the FDA, NCI and other regulatory authorities may review medical records and copy relevant research records in accordance with local laws.

Should direct access to medical records require a waiver or authorization separate from the subject's statement of informed consent, it is the responsibility of the Investigator to obtain such permission in writing from the appropriate individual.

12.4. Investigator Responsibilities

Investigator responsibilities are set out in the ICH guideline for Good Clinical Practice and the Code of Federal Regulations.

The Investigator will permit IRB/EC review and regulatory inspection(s) (e.g. FDA, EMEA, TPP), providing direct access to the facilities where the study took place, source documents and all other study documents.

The Investigator or a designated member of the Investigator's staff must be available at some time during auditing visits to review data and resolve any queries and to allow direct access to the subject's records (e.g. medical records, office charts, hospital charts, and study related charts) for source data verification. All study documents must be made available to the auditing representative so that the accuracy and completeness of study documents may be confirmed.

12.5. Protocol Amendments

If modification of the protocol is necessary, the modification must be confirmed in writing, and the Sponsor will inform the FDA in accordance with 21CFR 312; the Investigator will inform the IRB. Amendments that are administrative in nature do not require IRB approval but will be submitted to the IRB for information.

12.6. Suspension of Study

If conditions arise requiring further clarification before the decision to proceed with or terminate the study can be reached, the study will be suspended until the situation has been resolved.

APPENDIX A

Response Criteria and Survival Outcome Definitions

Timing of Response Evaluation

Response will be evaluated according to the Schedule of Evaluations listed above (Section 6.0)

Definition of Measurable Disease

- a. Measurable protein criteria of the serum are defined as serum M-protein of IgG, IgA, IgD, IgE Isotype ≥ 1.0 gm/dl (10.0 g/L). Measurable protein criteria of the urine are defined as urine M-protein (Bence-Jones Protein) > 200 mg/24 hours.
- Participants with IgM peaks must have either ≥ 20% bone marrow plasmacytosis or >3 lytic lesions on skeletal survey.
- c. Non-Secretory Disease: Participants without quantifiable M-proteins but with ≥20% bone marrow plasmacytosis will be assessed using plasma cell percentages. These participants will be evaluated for CR, no CR, and progression/relapse using the criteria above.

Response Criteria:

Multiple Myeloma: For the purpose of establishing one set of criteria for both Phase II and Phase III multiple myeloma studies, the following definitions will be used. These definitions are based on the International Uniform Response Criteria for Multiple Myeloma.

- a. **Measurable Disease**: Measurable, quantifiable protein criteria must be present. Acceptable protein criteria are:
 - Serum M protein ≥ 1 g/dL (≥ 10 g/L), quantified by using densitometry on serum protein electrophoresis (SPEP).

AND / OR

Urine M protein [Bence-Jones Protein] ≥ 200 mg/24 hrs (≥ 0.2 g/24 hrs), quantified by 24-hour urine protein electrophoresis (UPEP).

OR

 Patients who have both serum M protein levels < 1 g/dL AND urine M protein levels < 200 mg/24 hrs at baseline may be followed by serum free light chain (FLC) assay if involved free light chain level ≥ 10 mg/dL (≥ 100mg/L).

Oligosecretory and Non-secretory Disease: Patients that do not meet the criteria for measurable disease above may only be assessed for the following objective statuses: Stringent Complete Response, Stable, and Progression.

b. Objective Status:

Stringent Complete Response (sCR):

- Meets all of the criteria for Complete Response (CR) and
- normal serum free light chain ratio and

absence of clonal cells in bone marrow by immunohistochemistry or immunofluorescence **Complete Response (CR)**:

- Disappearance of all evidence of serum and urine M proteins on immunofixation electrophoresis studies and
- ≤ 5% plasma cells in bone marrow *and*
- disappearance of any soft tissue plasmacytomas

Very Good Partial Response (VGPR):

- Meets all of the criteria for Partial Response (PR) and
- Serum and urine M proteins detectable by immunofixation but not on electrophoresis or
- ≥ 90% reduction in serum M protein **and** urine M protein < 100 mg/24 hrs.

Partial Response (PR):

- If the patient had soft tissue plasmacytomas present at baseline and they were assessed at this disease assessment: ≥ 50% reduction in size of soft tissue plasmacytomas (see Appendix A; Notes h.)*and*
- If the patient had ≥ 30% plasma cells in bone marrow at baseline and a bone marrow biopsy was done: ≥ 50% reduction in plasma cells **and**
- ≥ 50% reduction in serum M protein **and** reduction in urine M protein ≥ 90% or to < 200 mg/24hr **or**
- If patient had serum M protein < 1 g/dL, urine M protein < 200 mg/24 hrs, and an involved serum free light chain level ≥ 10 mg/dL at baseline: ≥ 50% decrease in the difference between involved and uninvolved serum free light chain levels

Stable Disease (STA):

• Patient does not meet criteria for Stringent Complete Response, Complete Response, Very Good Partial Response, Partial Response, or Progression.

Progression (PROG): Any one or more of the following:

- Serum M protein increase ≥ 25% from baseline (or an increase of ≥ 1 g/dL if serum M protein was ≥ 5 g/dL at baseline), with an absolute increase of ≥ 0.5 g/dL or
- Urine M protein increase ≥ 25% from baseline, with an absolute increase of ≥ 200 mg/24 hrs or
- If patient had serum M protein < 1 g/dL, urine M protein < 200 mg/24 hrs, and an involved serum free light chain level ≥ 10 mg/dL at baseline: ≥ 25% increase in the difference between involved and uninvolved serum free light chain level, with an absolute increase of ≥ 10 mg/dL or
- Bone marrow plasma cell percentage increase ≥ 25% from baseline, with the absolute plasma cell % ≥ 10% or
- New bone lesions or soft tissue plasmacytomas, or definite increase in size of existing bone lesions or soft tissue plasmacytomas (see Appendix A: Notes h.) or
- Development of hypercalcemia (corrected serum calcium > 11.5 mg/dL or 2.65 mmol/L) that can be attributed solely to multiple myeloma

NOTE: If a disease assessment indicates that a patient is experiencing a Stringent Complete Response, Complete Response, Very Good Partial Response, Partial Response, or Progression, this should be confirmed by a second disease assessment and this should be done prior to the institution of any new therapy. The second disease assessment may be done at any time.

Notes:

- a. "M protein" may also be known by the following synonyms: M-spike, monoclonal protein, myeloma protein, monoclonal paraprotein, M-component.
- b. Urine M protein measurement is estimated using 24-hour urine protein electrophoresis (UPEP) only. Random or 24 hour urine tests measuring kappa and lambda light chain levels are not reliable and are not recommended.
- c. Patients with 'measurable disease' in both the serum and urine (serum M protein ≥ 1g/dL and urine M protein ≥ 200 mg/24h) at baseline need to be followed by both SPEP and UPEP for response assessment.
- d. Except for assessment of Complete Response, patients with 'measurable disease' restricted to the serum (serum M

protein \geq 1 g/dL and urine M protein < 200 mg/24h) at baseline may be followed by SPEP only. Likewise, except for assessment of Complete Response, patients with 'measurable disease' restricted to the urine (serum M protein < 1 g/dL and urine M protein \geq 200 mg/24h) at baseline may be followed by UPEP only.

- e. Patients with serum M protein ≥ 1 g/dL and/or urine M protein ≥ 200 mg/24h at baseline will be assessed for response based on SPEP and/or UPEP results only. Except for assessment of Stringent Complete Response, serum free light chain (FLC) assay response requirements are only applicable to patients who had serum M protein < 1 g/dL, urine M protein < 200 mg/24 hrs, and an involved serum free light chain level ≥ 10 mg/dL at baseline. A normal serum free light chain ratio is required for all patients for a Stringent Complete Response.
- f. To qualify for a Complete Response, both serum and urine immunofixation must be carried out and must be negative, regardless of the size of the baseline M protein in the serum or urine.
- g. Skeletal survey is not required for assessment of response unless clinically indicated, but is recommended once a year in clinical practice. Stringent Complete Response, Complete Response, Very Good Partial Response, Partial Response, and Stable Disease all require no known evidence of progressive or new bone lesions if radiographic studies were performed, but radiographic studies are not required to satisfy these response requirements.
- h. The size of the soft tissue plasmacytomas is defined as the sum of the products of the cross-diameters of each plasmacytoma. The size of the bone lesions will be determined in a similar manner. A definite increase in the size is defined as a ≥ 50% increase (and at least 1 cm²) of this sum.

Best Response: This is calculated from a sequence of Objective Status evaluations

Stringent Complete Response (sCR): An objective status of Stringent Complete Response on at least two sequential disease assessments. Only one bone marrow biopsy, done during one of these two disease assessments, is required to confirm the response.

Complete Response (CR): An objective status of Complete Response on at least two sequential disease assessments. Only one bone marrow biopsy, done during one of these two disease assessments, is required to confirm the response.

Very Good Partial Response (VGPR): An objective status of Very Good Partial Response on at least two sequential disease assessments.

Partial Response (PR): An objective status of Partial Response on at least two sequential disease assessments.

Unconfirmed sCR (UsCR): One objective status of Stringent Complete Response (based on evidence from serum and urine studies and, if drawn, bone marrow biopsy) but the confirmation studies are either not done, or when done, do not meet the requirements necessary to confirm response. This must be documented before progression and at least three weeks after registration.

Unconfirmed CR (UCR): One objective status of Complete Response (based on evidence from serum and urine studies and, if drawn, bone marrow biopsy) but the confirmation studies are either not done, or when done, do not meet the requirements necessary to confirm response. This must be documented before progression and at least three weeks after registration.

Unconfirmed VGPR (UVGPR): One objective status of Very Good Partial Response, but the confirmation studies are either not done, or when done, do not meet the requirements necessary to confirm response. This must be documented before progression and at least three weeks after registration.

Unconfirmed PR (UPR): One objective status of Partial Response, but the confirmation studies are either not done, or when done, do not meet the requirements necessary to confirm response. This must be documented before progression and at least three weeks after registration.

Stable / No Response (STA): At least one objective status of Stable at least three weeks after registration, but not qualifying as any of the above. If radiographic studies were performed there should be no known progressive or new bone lesions.

Increasing Disease (INC): First objective status recorded (other than Unknowns or those before three weeks) of Progression, provided this occurs within eight weeks of registration.

Inadequate Assessment. Response Unknown (NASS): Progression greater than eight weeks after registration and either all objective statuses prior to registration are unknown or the only known objective statuses occurred less than three weeks after registration.

Relapse: In patients with a confirmed response as described above, relapse is defined as the first occurrence of any of the following, reconfirmed by repeat analysis of serum and/or 24-hour urine M protein, done more than 2 weeks apart:

- a. Myeloma protein increase by more than 100% from the lowest level recorded on study, or a rise of 2.0 g/dl (this increase must be to a level > 1.0 g/dL if it is to constitute the sole manifestation of relapse).
- b. Myeloma protein increase above the response criteria for PR (see criteria for Partial Remission).
- c. Reappearance of M-protein in blood or urine not related to immune recovery or recent infection.
- d. Increase in the size and number of lytic bone lesions recognized on radiographs. New skeletal or MRI lesions, preferentially confirmed by fine needle aspirate.
- e. Myeloma related cytogenetic abnormalities.
- f. BM plasmacytosis > 10% or > 5% light chain restricted, non-diploid, plasma cells on clg/DNA.
- g. Hypercalcemia, not explained by any other cause.

Survival Outcomes

Overall Survival: measured as the time from initial registration to death from any cause.

Event-Free Survival: measured as the time from initial registration to progression/relapse of disease or death from any cause

